#### **Functional Exam-Based Outcomes**

**Balance.** Balance will be measured using the balance subscale of the Short Physical Performance Battery (SPPB). The SPPB has been used in multiple studies of cancer patients.[73-75] The SPPB balance subscale is a composite measure of timed feet together, semi-tandem, and tandem foot stands.[76] Results will be recorded in the **SPPB data collection form** 

Descending inhibition. Descending inhibition will be evaluated using a Conditioned Pain Modulation (CPM) test. The CPM test is a common test used in chronic pain studies in a wide variety of patient types, including those with CIPN, [27] diabetic neuropathy, [77] osteoarthritis, [78] fibromyalgia, [79] irritable bowel syndrome, [80] carpel tunnel syndrome, [81] and low back pain. [82] The CPM tests includes 2 temporary pain stimuli, a test stimulus that is administered before and after a conditioning stimulus. The difference in the result of the test stimulus before and after the conditioning stimulus is indicative of the efficiency of the participant's descending inhibitory pathways. The CPM test has demonstrated ability to distinguish between groups as expected [83] and intra-session reliability.[84] In this case the test stimulus will be pressure and the conditioning stimulus will be brief (up to approximately 30 sec -1 minute) immersion in cold water. Specifically, the participant's pressure pain threshold (PPT) (i.e., the point at which a pressure stimulus *first* becomes painful) is measured on the trapezius muscle 3 times (i.e., the test stimulus). Subsequently the participant is asked to immerse their right hand in ice water (~4°C) for 15 seconds (i.e., the conditioning stimulus), at which point they will be asked to rate the pain in their hand and then 3 subsequent pressure pain threshold measures will be taken on the trapezius muscle while the hand is held in the water. Participants will be told that they may remove their hand from the cold water before the 15 seconds has elapsed if it is too painful for them. If they remove their hand prior to the 15 seconds the post conditioning stimulus PPT measurements will be taken at that time. The temperature of the water will be monitored for consistency and to ensure it does not go below 4°C. Results will be recorded in the CPM data collection form.

**Lower-limb sensation threshold.** Lower limb sensation will be evaluated using a monofilament test threshold test. In the monofilament test, the participants are asked to close their eyes while each monofilament is applied (or not) to the dorsum of the big toe in random order 10 times (i.e., trials). With each trial, the participant is asked to state whether they think the filament touch their skin. For each set of 10 trials with a single monofilament, if the participant guesses correctly  $\geq$  9 times the next weaker monofilament is used. If the participant guesses correctly 7 or 8 times this filament is documented as the participant's sensation threshold. If the participant guesses correctly  $\leq$  6 times the next stronger filament is trialed. The participant's sensation threshold is the outcome of the test. Results will be recorded on the Scoring Sheet for the Lower Limb Sensation test and then entered in REDCap in the Lower-limb sensation threshold data collection form.

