(7) The proportion of participants who report, for the impression of change in CIPN symptoms question "very much improved", "much improved", "minimally improved", "no change", "minimally worse", "much worse", and "very much worse") will be compared between treatment groups using a Cochran Armitage Trend Test.

(8) The proportion of participants whose sensation threshold from the monofilament test improved will be reported together with the 95% confidence interval (CI) and tested against the null hypothesis of no improvement.

(9) Descriptive statistics and 95% CIs will be used to assess the percentage of participants and outcome assessors that correctly identify the group to which the participant was assigned as well as the basis for the guesses.

(10)Test, re-test reliability for the CPM test will be evaluated using Intraclass correlation coefficients (ICCs). Test, re-test reliability for the lower limb sensation threshold test will be measured using Kappa statistics.

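### The monofilament rule has no stop when a filament scoring 9 or more adjoins a weaker one scoring 6 or fewer, so the recorded threshold can be left to chance

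*Combined protocol and SAP*

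**What the plan says.** Section 5.4, under the functional exam-based outcomes, defines the test. Each set is ten trials with one filament, touch or no touch in random order, and the participant says each time whether there was a touch. The set score leads to one of three actions:

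- 9 or 10 correct: step down to a weaker filament;
- 7 or 8 correct, the only ending: "If the participant guesses correctly 7 or 8 times this filament is documented as the participant's sensation threshold";
- at most "6 times the next stronger filament is trialed".

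The section names no starting filament, no maximum number of sets and no action at the weakest or strongest filament. On recording it says: "Results will be recorded on the Scoring Sheet for the Lower Limb Sensation test". That sheet is not part of the documents. Section 4.4.1 (assessor training), Table 10 and section 10.6 add no stopping rule.

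The threshold enters two exploratory analyses. Item 10.6(8) reports the proportion of participants whose threshold improved, with a 95% confidence interval and a test against no improvement. In item 10.6(10), "re-test reliability for the lower limb sensation threshold test will be measured using Kappa statistics". The test is done at screening, baseline and Week 6.

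**The concern.** The three actions cover every score from 0 to 10, and only a 7 or 8 ends the test. A pass at 9 or more followed by 6 or fewer on the next weaker filament is the clearest threshold a participant can show, yet the rule does not stop there. It sends the assessor up, then down, then up again, until a 7 or 8 happens to occur. A participant who passes the weakest filament, or fails the strongest, has no defined next step.

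At stake are the meaning of the recorded value and the length of the test. An assessor facing a long alternation may improvise a stop, and sites could improvise differently. If only the final filament is kept, the value cannot be repaired afterwards.

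**Working it through.** The plan states no figure for this test, so there is none to reproduce.

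**Inputs.** From section 5.4: ten trials per set and cut-points at 6 or fewer, 7 to 8, and 9 or more. Assumed, because the documents give no response curve: success probability 0.5 per trial on an unfelt filament (guessing) and 0.90 to 1.00 on a felt one. The split of touch and no-touch trials is also not stated.

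**Step 1: one set.** Binomial(10, p):

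| p | 6 or fewer | 7 or 8 | 9 or more |
|---|---|---|---|
| 0.50 | 0.828 | 0.161 | 0.011 |
| 0.90 | 0.013 | 0.251 | 0.736 |
| 0.95 | 0.001 | 0.085 | 0.914 |
| 0.98 | 0.000 | 0.016 | 0.984 |
| 1.00 | 0 | 0 | 1 |

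**Step 2: the alternation.** Start on the weakest felt filament, with the next one unfelt. Let f be the chance of a 7 or 8 on the felt filament and u = 0.161 the chance on the unfelt one. Treat any other score as continuing between the two. Then

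- P(ends on the unfelt filament) = (1 − f)u / [1 − (1 − f)(1 − u)]
- mean sets = [1 + (1 − f)] / [1 − (1 − f)(1 − u)]

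For f = 0: the probability is 1 and the mean is 2 / 0.161 = 12.4 sets. For f = 0.085: 0.915 × 0.161 / (1 − 0.915 × 0.839) = 0.147 / 0.232 = 0.63, and 1.915 / 0.232 = 8.2 sets.

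An exact Markov chain over ten filaments, which allows moves beyond the pair, gives:

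| success on felt filament | ends on unfelt filament | mean sets |
|---|---|---|
| 1.00 | 100% | 12.3 |
| 0.98 | 91% | 11.3 |
| 0.95 | 64% | 8.2 |
| 0.90 | 32% | 4.7 |

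In the first row, 12.3 sets is 123 trials; 41% of runs are still going after 10 sets and 17% after 20. Simulation on a 20-filament ladder with varied true thresholds puts the 95th percentile at about 35 sets.

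**Step 3: graded detection.** Let success rise smoothly from 0.5 to 1 along a normal curve, with SD in filament steps. The chance of a 9-or-more / 6-or-fewer pair on one pass over the two filaments around threshold, and the mean number of sets, are:

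| SD | chance of the pair | mean sets |
|---|---|---|
| 0.2 | 0.82 | 13.9 |
| 1 | 0.25 | 4.4 |
| 2 | 0.13 | 3.3 |
| 3 | 0.10 | 2.7 |

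The problem fades as the curve flattens.

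**Step 4: no guessing.** If a participant always answers no when nothing is felt and the split is fixed at 5 and 5 (assumed), every unfelt set scores exactly 5. With perfect success on the stronger filament, the test never ends.

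**Step 5: with a stop at the pair, recording the stronger filament.** For a sharp threshold, starting on the weakest felt filament, an unfelt one is recorded only if the first unfelt set scores 7 or more: 0.161 + 0.011 = 0.172. Averaged over starting points, some of which climb through several unfelt filaments, the share is about 24%. The mean is about 2 to 3 sets.

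**Step 6: effect on the two analyses.** With no true change and two independent tests, false improvement = (1 − exact agreement) / 2.

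| threshold | agreement as written | agreement with stop | false improvement as written | false improvement with stop |
|---|---|---|---|---|
| sharp, no lapses | 0.86 | 0.63 | 7% | 18.5% |
| sharp, 5% lapses | 0.45 | 0.60 | 27.5% | 20% |

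**The case against.** **A lucky guess is not the only exit.** A reader might infer that the loop always ends on a filament the participant cannot feel. That needs perfect success on the stronger filament and pure guessing one step below. A lapse to 7 or 8 on the felt filament also ends the test: 36% of runs at success 0.95 and 68% at 0.90. Nor does one score of 6 or fewer prove that a filament is unfelt, since at a true success of 0.65 it happens 49% of the time. This stands.

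**For graded curves the written rule is reasonably centred.** A reader might count every filament detected less than half the time as an error. With guessing, 50% detection means 75% correct, which is what a score of 7 or 8 targets, so a good estimator falls below that point about half the time. Measured against it, the written rule's mean error is only about 0.1 to 0.3 steps towards the weaker side. This stands, and no error share is claimed here for graded curves.

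**A constant offset cancels in change and agreement.** Largely true. With a perfectly sharp threshold the written rule is wrong in a consistent way, which is why its retest agreement is high.

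**The scoring sheet or the training may hold a stop.** That cannot be checked. Section 5.4 nevertheless states a complete set of actions that does not contain one, so any rule held elsewhere should also appear there.

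**Conclusion.** The gap is real and can be read directly from section 5.4: a 9-or-more / 6-or-fewer pair does not end the test, and the ends of the kit are not covered. The test then finishes by chance on either filament, often on the one not felt. How often depends on response curves that the documents do not give:

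- perfectly sharp threshold: about 12 sets, and an unfelt filament every time;
- 5% lapses on felt filaments: about 8 sets, and an unfelt filament in about 65% of runs;
- gradual threshold: about 3 sets, and a small problem.

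The effect is confined to exploratory analyses 10.6(8) and 10.6(10) and to visit length. The primary CIPN20 analysis, the secondary symptom analyses and the sample size do not use this test. A reader might go further and call the improvement proportion or the kappa invalid. The documents do not support that, because retest error for gradual thresholds is similar with or without a better stop. This is a change to consider, not a condition for the trial.

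**What to change.** Add to section 5.4, the scoring sheet and assessor training: *Stop when a filament has scored 9 or more and the next weaker has scored 6 or fewer, and record the stronger of the two. If the weakest filament scores 9 or more, or the strongest scores 6 or fewer, record that limit.* The 7-or-8 rule stays as it is.

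The cost is a short addition to the text and training. The statistical price is the loss of retest agreement for a perfectly sharp threshold without lapses shown in step 6; with 5% lapses agreement improves.

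A stricter option also counts 7 or 8 as a fail, so that only 9 or more passes. That cuts the unfelt share for a sharp threshold to about 2% and raises agreement for sharp and steep thresholds. However, it redefines the threshold as about 0.5 to 1.1 filament steps stronger and lowers agreement for gradual ones (about 0.31 against 0.40). It should be adopted only if that redefinition is intended.

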#### Feasibility Outcomes

Proportion of screened participants who enroll in the study will be extracted from study records.

**Outcome measure completion rates** for PROs, balance measures, CPM tests, lower limb sensation test, and Quell Health App usage will be extracted from study records. The proportion of total instances that each outcome was completed appropriately in the baseline and endpoint visits will be evaluated.

**Treatment adherence** will be evaluated using data downloaded from the TENS device after the Week 6 Visit (i.e., the number of treatment sessions/day and the time that the device was in contact with the skin). The following summaries regarding adherence will be explored: (1) The mean number of study days that each participant used the device for at least the amount of time prescribed based on data downloaded from the device, (2) the proportion of participants who used the device for at least 5 hours per day on at least 70% of the days based on data downloaded from the device.

Potential reasons for low treatment adherence will be captured using a Qualitative Feedback Questionnaire.

**Reasons for ineligibility or refusal to enroll captured** on the **Screening log** will be evaluated to determine if changes in the study design could greatly improve recruitment rates of a future study.

#### 5.5 Potential Risks

There are four potential risks associated with participation in the study

(1) Physical harm associated with the intervention. There is a small risk of skin irritation at the site where the electrodes attach the TENS device to the skin. In addition, 3 of 26 participants in our pilot study reported mild worsening of neuropathy symptoms or new, abnormal sensations after starting the TENS device. Although it is unknown whether these symptoms were a physiological or psychosomatic consequence of the TENS treatment, all symptoms disappeared after stopping the TENS treatment for 2 participants. One participant felt that the new sensations were acceptable considering the perceived benefits of the TENS treatment and decided to continue using the TENS device.

(2) Physical harm associated with the assessments. The conditioned pain modulation test involves evoking pain using pressure from an algometer and temporary immersion in cold water. These pains are temporary.

(3) Emotional distress. The assessments explore participants' feelings regarding their CIPN symptoms and associated functioning. Some participants may become distressed when they think about these topics.

(4) Loss of confidentiality. Participants' data from assessments and clinical factors extracted from the medical record will need to be stored. A small chance exists that a confidentiality breech will result in participants' sensitive health information being made available to parties outside the research team. However, participants' names and contact information will be kept separately from the study data to minimize the chance of loss of confidentiality. If information from this study is published or presented at scientific meetings, participants' names and other personal information will not be used.

#### 5.6 Emergency Study Device Disclosure

Unblinding of the study device is ONLY permitted in the case of serious and unexpected adverse events that are definitely, probably or possibly associated with the use of the study device AND if knowledge of

the study treatment arm received is necessary for interpreting the medical event and related treatment of that medical event. In such cases, the treating MD or their designee can be given the treatment group assignment from the unblinded coordinator. This event needs to be documented and the IRB notified within seven days. Documentation should be sent to the email address below and include participant ID number, site investigator, and reason for unblinding in the message:

#### [name] [name] [contact]

Participants that require emergency study device disclosure will discontinue use of the study device. The research team may continue to follow the study participant for assessment data with participant and treating provider approval.

# 5.7 Costs to the Participant

If participants do not have a data plan on their cellular phone or device, they will incur data charges associated with using the App and transferring the data to the cloud if they are not connected to a Wi-Fi source. If participants do have a data plan, it is very unlikely that they will incur extra charges for data usage because the approximate amount of data used by the App if it is opened 5 times per day is 2.5Mb, which is a fraction of the minimally available cellular data plan (i.e., 1GB) and home internet service plans (i.e., 1000GB).

## 5.8 Payment for Participation

Participants will not receive payment for the study. However, all participants will receive, for free, an active TENS device after completion of the study that they can keep after the end of the study.

## 5.9 Contraindications

With the exception of entry criteria listed in **Section 3**, there are no restrictions on who can safely use TENS. Participants should not get the TENS device wet and therefore should not, for example, wear it in the shower or when swimming. In addition, the TENS device should not be worn continuously for more than 12 hours to minimize potential skin irritation. Finally, the TENS device should not be used while driving.

#### 5.10 Concomitant Medications

There are no limitations on concomitant medications taken at stable dosages (see eligibility criteria in **Section 3.2**).

#### 5.11 Adherence

Treatment adherence will be monitored during the study using data downloaded from each participant's Quell Health Account. The Quell Health Account will be set up at the baseline visit using a de-identified, unique Study Email address created for the study to protect participants' privacy. These data will be used to provide real-time feedback to participants and in turn hopefully optimize adherence. Treatment adherence will be evaluated as an outcome of the study using data downloaded after the Week 6 Visit when the coordinator links the App (i.e., the number of treatment sessions/day and the time that the device was in contact with the skin).

## 6. STUDY DEVICE DISTRIBUTION

# 6.1 Availability

Active and placebo TENS devices will be supplied by the URCC NCORP Research Base.

# 6.2 Distribution

The active and placebo TENS devices will be supplied by the URCC Research Base. Each device includes a package of 2 electrodes. A second package of 2 electrodes will be sent with each device. Four electrodes should last approximately 8 weeks (2 weeks each). Extra electrodes can be requested from the Research Base if necessary. Devices will only be released to URCC NCORP Research Base affiliates approved to participate. Upon approval to participate, 1 active and 1 placebo device will be shipped to each site. Once a device is distributed to a participant, the site Investigator, or their authorized designee should request a replacement device be shipped to their site so that each site has 1 active and 1 placebo device in stock at all times. If more than 1 participant is enrolled on the study and both participants are completing the baseline week at the same time, the site Investigator or designee can request a second pair of devices to ensure that the correct device will be available for the participant at the Baseline visit. Devices are requested by emailing the URCC NCORP Research Base and should include complete shipping and contact information and device group (i.e., orange or blue dot sticker). All TENS devices used by participants during the study will be returned to the URCC NCORP Research Base within 3 months of completion of the 6 Week Visit.

[name] URCC [contact] [contact]

## 6.3 Device Accountability

The NCORP site, and responsible party designated at the site, must maintain a careful record of the inventory and disposition of all devices and packets of electrodes received from the URCC NCORP Research Base using the Investigational Device Accountability Record. All receipt and dispensation of study devices should be recorded, including date, participant ID# and initials, serial number from the back of the device, and blinded device label. All unused devices will be returned to URCC at the end of the study.

## 6.4 Packaging and Labeling

Neurometrix will provide to the Research Base the devices in identical packaging with a key that will identify the active and placebo devices via the serial numbers that [name] ([name]) will have access to. URCC Research Base staff will apply the coded labels (i.e., orange or blue dot stickers). Neither the Study Chair, Co-chairs, nor statisticians will have access to the label key so they will remain blinded until after the primary and secondary analyses are completed.

## 6.5 Storage

The devices will be stored at room temperature. Study devices will be stored away from heat and moisture. Study devices will be stored in a secured location that is only accessible by approved study personnel.

# 7. CRITERIA FOR EVALUATION AND ENDPOINT DEFINITION

## 7.1 **Primary Endpoint**

The primary study endpoint is CIPN as measured by the mean European Organisation for Research and Treatment of Cancer-CIPN20 (EORTC-CIPN20) [54] score after 6 weeks of device use.

#### 7.2 Off-Device Criteria

Participants may stop using the study device for the following reasons: (1) completed the protocolprescribed intervention, (2) adverse event or serious adverse event, or (3) if they want to for any reason. Participants will continue to be followed, if possible, in order to collect endpoint data according to the schedule of study procedures (see **Section 5.3**).

### 7.3 Off-Study Criteria

The following are among the reasons that participants may leave the study: (1) the protocol intervention and any protocol-required follow-up period is completed, (2) adverse event/serious adverse event, (3) lost to follow-up, (4) withdrawal of consent, (5) death, (6) determination of ineligibility (including eligibility error), (7) pregnancy, or (8) if they want to for any reason.

### 8.0 REPORTING ADVERSE EVENTS

The prompt reporting of adverse events is the responsibility of each investigator engaged in clinical research, as required by federal regulations. Adverse events must be described and graded using the terminology and grading categories defined in the NCI's common terminology criteria for adverse events (CTCAE), version 5.0. The CTCAE is available at

https://ctep.cancer.gov/protocoldevelopment/electronic applications/ctc.htm#ctc 50.

The relationship to the study intervention and the severity of each adverse event as judged by the investigator must be recorded. Attribution to protocol treatment for each adverse event must be determined by the investigator and reported on the required forms, using the codes provided.

#### 8.1 Definitions

Adverse event (AE) is any untoward medical occurrence associated with the use of a medical product, which does not necessarily have a causal relationship with its use. An adverse event can be any unfavorable and unintended sign (including abnormal laboratory test results), symptom, or disease temporally associated with the use of the study product or not considered related to the study product. The relationship of each adverse event to the study interventions must be recorded as one of the choices on the scale described below.

**Table 6. Attribution**. Categories to define the relationship between the adverse event and study device/intervention.

ATTRIBUTION	DESCRIPTION
Unrelated	The AE is clearly NOT related to the study device /intervention
Unlikely	The AE is doubtfully related to study device /intervention
Possible	The AE may be related to study device/intervention
Probable	The AE is likely related to study device/intervention
Definite	The AE is clearly related to study device/intervention

